- The patient cohort will be stratified by pre-treatment groups and may include injectable, oral and infusion DMTs used in RMS: interferon beta-1a (Avonex[®], Rebif[®]), interferon beta-1b (Betaseron[®], Extavia[®]), glatiramer acetate (Copaxone[®], generic glatiramer acetate), peginterferon beta-1a (Plegridy[®]), teriflunomide (Aubagio[®]), fingolimod (Gilenya[®], including generic forms of fingolimod), dimethyl fumarate (Tecfidera[®], including generic forms of dimethyl fumarate, Vumerity[®] (diroximel fumarate)), natalizumab (Tysabri®), and ocrelizumab (Ocrevus®).
- Patients fulfilling the inclusion criteria, including genotyping, will undergo immediate
 conversion (please see below for exceptions) to siponimod, with "immediate" defined as
 cessation of the existing DMT and initiation of siponimod within 24 hours, followed by
 subsequent 5-day dose titration. Per inclusion criteria and screening phase testing
 requirements, fingolimod patients will undergo all required screening and/or baseline
 testing, including genotyping for CYP2C9*1*1.
 - Patients converting specifically from teriflunomide will undergo accelerated elimination prior to converting to siponimod over 11-14 days to allow for adequate drug elimination and minimize drug-drug interactions, in line with the Aubagio ® USPI.
 - Patients converting from fingolimod will immediately convert to siponimod maintenance dose of 2mg, with no dose-titration.
 - Patients treated with infusion DMT natalizumab (Tysabri®) will undergo at least a 4
 week washout period at the time of consent, prior to converting to dose-titrated
 siponimod.
 - Patients treated with infusion DMT ocrelizumab (Ocrevus®) will undergo at least 14
 week washout period at the time of consent, prior to converting to dose-titrated
 siponimod.
- All patients initiating siponimod treatment, expect those converting from fingolimod, will be titrated over 5 days to achieve a maintenance dose of 2mg by Day 6 with the following schedule of siponimod:

Figure 3-1 Siponimod Target Daily Dose

[figure not shown]
Tit	tration Dose
Day of	Target
Treatment	Dose
1	0.25 mg
2	0.25 mg
3	0.5 mg
4	0.75 mg
5	1.25 mg
Mair	itenance Dose
Day of	Target
Treatment	Dose
6 and	2 mg
beyond	

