Assessment schedule Table 8-1 lists all of the assessments and when they are performed. All data obtained from these assessments must be supported in the patient's source documentation.

Pre-treatment strata drug name	Washout Interval Guidance
Interferon-beta/glatiramer acetate	None; immediate conversion to dose-titrated siponimod
Fumarates (dimethyl fumarate, diroximel fumarate)	None; immediate conversion to dose-titrated siponimod
Teriflunomide	11-14 day accelerated elimination protocol (Appendix 6) prior to starting dose-titrated siponimod
Fingolimod	None; immediate conversion to siponimod maintenance dose 2mg
Natalizumab	Last natalizumab dose at least 4 weeks prior to screening
Ocrelizumab	Last ocrelizumab dose at least 14 weeks prior to screening

No washout is required for patients converting from interferon-beta or fumarates (dimethyl fumarate, diroximel fumarate) prior to starting dose-titrated siponimod.

An accelerated elimination (Appendix 6) interval will be required for patients taking teriflunomide before the patient can start treatment with siponimod. At least 2 weeks with successful accelerated teriflunomide elimination procedure as described in the product label should be conducted for these patients. If accelerated elimination is not possible, the patient cannot participate in the study.

No washout period or titration regimen is required for patients converting from fingolimod to siponimod and CYP2C9 *1/*1, *1/*2, or *2/*2 genotyped patients will start directly on 2mg maintenance dose upon entering the treatment period.

At least a 4 week interval will be required for patients converting from natalizumab.

At least a 14 week interval will be required for patients converting from ocrelizumab.

- On Visit 1 (Day 1, baseline), patients who met eligibility criteria will have pre-dose body temperature, respiration rate, blood pressure, ECG and heart rate assessed prior to initial dose of siponimod. 6 hours after the initial dose of siponimod, heart rate will be measured again. The study site personnel will instruct the patient on how to obtain the 6-hour post dose heart rate. Pre-dose ECG may be obtained via vendor-supplied ECG vest and pre-dose HR may be obtained either manually (see below for guidance) or via ECG. Post-dose HR may be obtained via vendor-supplied HR monitoring device.

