- X = assessment to be recorded in the clinical database or received electronically from a vendor
- S = assessment to be recorded in the source documentation only
- 1. All baseline assessment are to be performed prior to siponimod dosing
- 2. Take another heart rate measure 6 hours post Day 1 dose (a Novartis-supplied portable heart rate monitor patch)
- 3. Patients currently taking or having taken teriflunomide in past 8 months will require a washout per label instructions prior to the baseline.
- 4. Patients may opt in or opt out of completing this questionnaire (optional).
- 5. Only SAEs and SAE related medications are to be collected.
- 6. OCT can be done 5 days prior to treatment or on Day 1 prior to treatment refer to Appendix 8.
- 7. ECG to be performed pre-dose on Day 1 (baseline) however, if the ECG assessment meets criteria in the protocol section 8.4.2., dosing cannot be initiated.
- 8. Neurological Exam refer to the protocol section 8.4 Table 8-2 for more details.

- 10. CD19+ titers only for patients previously exposed to ocrelizumab DMT.
- 11. Fingolimod patients will receive an additional telephone call from site staff at the end of BSL (Day 1) as part of additional safety measures.
- 12. There is no longer an ECG at Day 7 (visit 2). Therefore, visit 2 has been grayed-out and no longer applicable.

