16.5 Appendix 5: Assessing Immunity to Varicella

(https://www.cdc.gov/chickenpox/hcp/immunity.html)

Evidence of immunity to varicella includes any of the following:

Documentation of age-appropriate varicella vaccination;

- Preschool-age children (i.e., age 12 months through 3 years): 1 dose
- School-age children, adolescents, adults: 2 doses
- Laboratory evidence of immunity or laboratory confirmation of disease
- Birth in the United States before 1980 (Should not be considered evidence of immunity for health care personnel, pregnant women, and immunocompromised persons)
- Diagnosis or verification of a history of varicella or herpes zoster by a health care provider

To verify a history of varicella, health care providers should inquire about:

- an epidemiologic link to another typical varicella case or to a laboratory confirmed case, or
- evidence of laboratory confirmation, if testing was performed at the time of acute disease

Persons who have neither an epidemiologic link nor laboratory confirmation of varicella should not be considered as having a valid history of disease. For these persons, a second dose of vaccine is recommended if they previously received only one dose. If a health care provider verifies the diagnosis based on the above criteria, then vaccination is not needed

16.6 Appendix 6: Teriflunomide Accelerated Elimination Program (for patients treated with teriflunomide at screening or within 8 months prior to screening)

All patients treated with teriflunomide at screening or within 8 months prior to screening should undergo accelerated teriflunomide elimination program. This can be done anytime during the Screening Period if a switch in therapy for the patient is imminent or during the Treatment Period, Visit 1, after all inclusion criterion are met by the patient.

Recommended rapid elimination procedure is the administration of oral cholestyramine 8 g three times per day for 11 days. If patients do not tolerate this regimen, then the dosage may be reduced to 4 g three times per day. Teriflunomide levels are not required for this study however could be completed as part of standard of care.

If tolerability issues persist, cholestyramine administration does not need to occur on consecutive days unless there is an acute need to lower teriflunomide levels.

As an alternative to cholestyramine, oral activated charcoal administered as 50 g twice a day for 11 days may be used.

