### **2.3.1 Patient disposition**

Screening phase disposition and study phase disposition will be summarized.

The number and percentage of patients screened, screened passed and screen failed will be summarized for all the screened patients for the screening phase disposition.

For the study phase disposition, the overall number of patients who are screened passed i.e. entered into the study, completed the study and discontinued from the study (and/or treatment) will also be summarized with reasons for premature discontinuation on all enrolled patients.

Patient identification number and whether they completed or discontinued from the study (and/or treatment) will be listed, with date of last dose and primary reason for premature discontinuation.

For each protocol deviation (PD), the number and percentage of patients for whom the PD applies will be tabulated. A separate listing will be provided for the details on the patient identifier having met a specific PD.

The PD's will be distinguished in the below 5 categories as applicable:

- Selection Criteria Not Met - Inclusion/Exclusion criteria

- Patient Not Withdrawn As Per Protocol - Withdrawal criteria met but patient not withdrawn
- Treatment Deviation - Wrong treatment or incorrect dose
- Prohibited concomitant medication
- Other

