TRT03	treatment with Immunosuppressive/chemotherapeutic medications or procedures and hematopoietic stem cell transplantation but study treatment is not discontinued or interrupted	49
TRT04	Patient took Monoclonal antibodies targeting the immune system, including natalizumab, rituximab, ofatumumab, ocrelizumab and alemtuzumab but study treatment is not discontinued	49
TRT05	Patient took any other immunomodulatory or disease modifying MS treatment but study treatment is not interrupted	49
TRT06	Used any concomitant medication which inhibits cardiac conduction, e.g. verapamil-type and diltiazem-type calcium channel blockers or cardiac glycosides but study treatment is not discontinued	49
TRT07	Used Potent inducers of CYP2C9 but study treatment is not discontinued	49
COMD01	Patient took prohibited medication	49
OTHER01	Washout period is not there for taking teriflunomide before the patient can have their Day 1 visit (baseline) and start treatment with siponimod	49
OTHER02	Patients met eligibility criteria but does not have pre-dose body temperature; respiration rate; blood pressure; heart rate assessed	49
OTHER03	Study drug taken on the day of EOS	49
OTHER04	Pre-Dose vital signs; pre-dose ophthalmic exam; pre-dose ECG; screening labs (with exception of [REDACTED]); neurological exam	49
OTHER05	On-study Neurological exam not performed	49
OTHER06	Ophthalmology monitoring procedures not followed	49
OTHER07	Patient missed two consecutive lab assessments (with exception of [REDACTED])	49
OTHER08	Missed visit due to COVID-19	49
OTHER09	Visit done outside of study site due to COVID-19	49
OTHER10	Assessment / procedure changed due to COVID-19	49
OTHER11	Discontinuation due to COVID-19	49
TRT08	Post-dose cardiac monitoring not performed per protocol	49

TRT09	Study Drug Interruption of 4 or more consecutive days and re-started without first dose monitoring	49
TRT10	Drug supply method changed due to COVID-19	49
TRT11	Treatment not given due to COVID-19	49
OTHER12	Study Informed consent process not followed	49
OTHER13	SAE not reported to Sponsor in 24 hrs	49
OTHER14	Sample analyzed after withdrawal of consent	49

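### Appendix 6 lets teriflunomide elimination be done at Visit 1, the first-dose day, although Table 8-1 footnote 3 and SAP deviation OTHER01 require washout before it

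*Protocol*

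**What the plan says.** Appendix 6 of the protocol applies to anyone on teriflunomide at screening or within the 8 months before it. It recommends an 11-day course of cholestyramine or activated charcoal. It gives two times for the course: any point in the Screening Period if a switch is imminent, "or during the Treatment Period, Visit 1, after all inclusion criterion are met by the patient". Exclusion criterion 12 and Section 8 both send sites to this appendix.

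Elsewhere the timing is different:

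- Section 3 has elimination done "prior to converting to siponimod over 11-14 days to allow for adequate drug elimination and minimize drug-drug interactions".
- The washout table in Section 8 asks for an "11-14 day accelerated elimination protocol (Appendix 6) prior to starting dose-titrated siponimod", and the text below it says that the "interval will be required for patients taking teriflunomide before the patient can start treatment with siponimod".
- Footnote 3 to Table 8-1 says that these patients "will require a washout per label instructions prior to the baseline".
- SAP Table 5 lists as deviation OTHER01: "Washout period is not there for taking teriflunomide before the patient can have their Day 1 visit (baseline) and start treatment with siponimod".

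Protocol 6.3.2 has siponimod given on Day 1 at Visit 1. SAP 2.1.1.3 defines Visit 1 as the day of the first dose, and SAP 2.1.1.2 defines Day 1 as the date of first administration.

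**The concern.** A course of 11 days or more cannot both be done at Visit 1 and be finished before Visit 1. A site that follows Appendix 6 literally must either give siponimod while elimination is under way, which Section 8 bars, or put off the first dose. Either way it departs from footnote 3.

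Appendix 6 is the text that sites work from, and its Visit 1 option is attractive because nobody is washed out before eligibility is settled. Teriflunomide levels are not required, so no mandatory laboratory check would show incomplete elimination.

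The matter at stake is patient safety at drug start and the clarity of early data. Section 3 gives adequate elimination and fewer drug-drug interactions as the reasons for eliminating teriflunomide first. Overlap would cover the Day 1 heart-rate assessment, which is a secondary endpoint also summarised by prior DMT (SAP 2.6.1.2), as well as the titration and the first 2 mg doses. The primary endpoint rests on suspected relatedness to siponimod. In that window the judgement would be harder, because the elimination agent and residual teriflunomide would be competing explanations.

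**Working it through.** **1. The timing rules side by side**

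| Place | When elimination happens | Visit 1 option compatible? |
|---|---|---|
| Appendix 6 | Screening, or Visit 1 | It is the source of the option |
| Table 8-1 footnote 3 | Before baseline | No: baseline is Visit 1 |
| SAP OTHER01 | Before the Day 1 visit and siponimod start | No: absence of prior washout is a deviation |
| Section 3 | Before converting to siponimod | Only if the dose is not given at that visit |
| Section 8, table and text | Before siponimod starts | Only if the dose is not given at that visit |

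The conflict with footnote 3 and OTHER01 is direct. The conflict with Sections 3 and 8 depends on dosing at that visit, which is what Visit 1 means.

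**2. If the site doses on schedule.** A course of L days started on Day 1 covers Days 1 to L. With one dose a day it overlaps L doses. Teriflunomide patients are titrated on Days 1 to 5 and take 2 mg from Day 6, so L − 5 of those doses are at 2 mg.

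- L = 11: 11 doses, 5 in titration and 11 − 5 = 6 at 2 mg.
- L = 14: 14 doses, 5 in titration and 14 − 5 = 9 at 2 mg.
- Course finished before Day 1: no overlap.

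**3. If the site defers the dose.** Under SAP 2.1.1.2 and 2.1.1.3, Day 1 and Visit 1 move to the actual first-dose date. The visit where elimination began is then no longer Visit 1. Assessments tied to first dosing, such as the pre-dose ECG and the OCT (allowed up to 5 days before treatment), must be done or repeated at the actual first-dose visit.

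**4. Scale against the primary estimate.** The plan's stated precision, at an assumed rate of 45%, reproduces with half-width = 1.96 × √(0.45 × 0.55 / n):

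- n = 300: 5.6 points.
- n = 400: 4.9 points.

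One patient moves the overall related-event rate by at most 100/300 = 0.33 or 100/400 = 0.25 points. The documents give no current size for the teriflunomide subgroup. If it held 20 to 50 patients (an assumption), one patient would move that subgroup's rate by at most 100/20 = 5 to 100/50 = 2 points.

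**5. Does elimination fit in screening?** Screening lasts about 28 days. An 11-day course leaves 28 − 11 = 17 days and a 14-day course leaves 28 − 14 = 14. Appendix 6 allows non-consecutive dosing. On an assumed alternate-day schedule, 11 dosing days span 2 × 11 − 1 = 21 days and leave 7.

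**The case against.** The strongest reply is that Appendix 6 never says siponimod may be given during elimination. Section 8 requires the interval first and shuts out patients for whom elimination is not possible. A site reading both would confirm eligibility, run the course and then dose, which satisfies Sections 3 and 8. This stands, and it limits the harm to sites that use the Visit 1 option and also overlook Section 8. It does not rescue the clause, which still breaches footnote 3 and falls at a visit defined by the first dose.

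A second reply is that the Washout row of Table 8-1 carries its mark, S, in the Baseline column, which could suggest washout at that visit. S means recorded in source documents only, and the row's own footnote places washout before baseline. The mark is best read as confirmation that washout was done. Column positions in the extracted table may also be unreliable.

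A third reply is that overlap with the previous DMT is part of the design. Section 4.1 names overlapping immune effects as something to assess, and interferon, glatiramer acetate, fumarate and fingolimod patients convert with no washout. The agent used for elimination is recorded in the eCRF and medications carry start and end dates (SAP 2.4.2), so an unfinished course could be found. That is fair, and it means that attribution would be harder rather than impossible. For teriflunomide, however, the protocol chose elimination first and gave its reason.

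Two stronger readings are tempting. A reader might infer that Appendix 6 authorises co-administration; it does not. A reader might also infer that a deferred first dose falls days outside the Visit 1 window. Because the SAP counts Day 1 from first administration, the day count moves with the dose, so the documents do not support that count.

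**Conclusion.** The concern holds as an internal contradiction in operational text. The Visit 1 option conflicts directly with Table 8-1 footnote 3 and OTHER01, and it conflicts with Sections 3 and 8 if siponimod is given at that visit. Co-exposure ranges from none to 11 doses (11-day course) or 14 doses (14-day course). The upper figures assume that the course starts on Day 1 and that dosing goes ahead on schedule against Section 8. How many patients this concerns is unknown and may be zero.

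A reader might infer bias in the primary result. The documents do not support a material effect on the overall rate, given at most 0.25 to 0.33 points per patient against a half-width of 4.9 to 5.6. Nor does any analysis set change: OTHER01 carries code 49, which means that the deviation is reported and the patient stays in all analyses. Patients with no washout before Day 1 are already visible, since "For each protocol deviation (PD), the number and percentage of patients for whom the PD applies will be tabulated", with a separate listing. OTHER01 does not clearly cover a course begun but unfinished by Day 1.

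The change is still worth making, because it protects patients at drug start and costs little.

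**What to change.** Replace the timing sentence in Appendix 6 with:

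> This is done during the Screening Period, if a switch in therapy is imminent or once all other eligibility criteria are met. The full course must be completed before the first siponimod dose, and Visit 1 (Day 1) is scheduled only after completion, extending the approximately 28-day screening period if needed.

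This removes the Visit 1 option and keeps both conditions that Appendix 6 now sets. The eligibility condition should stay, so that patients are not washed out and then fail screening. Across all strata, 570 − 400 = 170 to 570 − 300 = 270 of those screened (30% to 47%) are not expected to enrol. The documents give no figure for teriflunomide patients alone.

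Extend OTHER01 to: *accelerated elimination absent or not completed before Day 1*.

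As an optional clarification, align "At least 2 weeks with successful accelerated teriflunomide elimination procedure" in the Section 8 text with the 11-14 days given in Section 3 and the Section 8 table. The phrase can be read as an interval that contains an 11-day course, so this is tidying.

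The cost is one sentence and one deviation text, with no new data. The downside is a tighter or slightly longer screening period for teriflunomide patients, mainly those who take the course on non-consecutive days. Table 8-1 already repeats laboratory tests, vital signs and the ECG at Visit 1, so a longer screening period does not leave those baseline values out of date.

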16.7 Appendix 7: Recommendations for the management of bradycardia

Initiating treatment results in a decrease in HR. If any of the following abnormalities are present after 6 hrs. (even in the absence of symptoms), additional monitoring should be conducted:

• Day 1: HR 6 hrs. post-dose <45 bpm

If post-dose symptomatic bradycardia, bradyarrhythmia, or conduction related symptoms occur, or there is evidence of new-onset second-degree or higher AV block or QTc ≥500 msec, initiate appropriate management; monitor ECG and symptoms until resolved if no pharmacological treatment is required.

The study site personnel should be particularly mindful of patients who have a low pulse at baseline (spontaneously or through drug-induced β-receptor blockade), prior to administration of the study drug. A cardiologist should be consulted if needed.

Atropine (subcutaneous or intravenous) is recommended as the first-line treatment of bradycardia, up to a maximum daily dose of 3 mg.

Furthermore, the common guidelines for treatment of bradycardia (e.g. ACLS guidelines) should be followed as appropriate:

- In case of clinical symptoms of bradycardia, administration of atropine 1 mg, with repeated administration in 3-5 minutes is recommended.
- If heart rate and/or blood pressure remain unresponsive, consider administration of dopamine drip 5-20 ug/kg/min or epinephrine drip 2-10 ug/min.
- Transcutaneous pacing may also be considered.
- In the setting of decreased blood pressure, isoproterenol should be avoided or used with caution.
- If a patient requires treatment for bradycardia/bradyarrhythmia during the first dose, the patient should be hospitalized for overnight monitoring and this monitoring procedure should be repeated for the second dose of study drug.

16.8 Appendix 8: Guidelines for Ophthalmic examination and management of Macular Edema

A complete ophthalmic examination and Optical Coherence Tomography (OCT) assessment are scheduled at baseline (Day 1) and Visit 4 (Day 84), as indicated in the assessment schedules for both CP study assessments (Table 8-1).

This appendix provides details of the ophthalmic examination requirements in the study.

A standard visual acuity chart with equal space between letters and between lines should be used for the visual acuity assessment. As noted in Section 8.4.5., the OCT machine used should preferably not be changed during the course of the study to allow for comparison of central foveal thickness within each patient across time points.

(1) Ophthalmic monitoring for general MS population Baseline visit:

At the baseline visit this eye examination will include;

- ophthalmic history
- best corrected visual acuity measurement
- ophthalmoscopy (may include contact lens biomicroscopy to examine the macula and optic disc).
- measurement of central foveal thickness by OCT (required for all patients regardless of the results of visual acuity or ophthalmoscopy).

N.B. Ophthalmic findings should be recorded.

If there is a suspicion of macular edema by ophthalmoscopy and increased central foveal thickness by OCT, then a fluorescein angiogram may be performed (at the discretion of the ophthalmologist). Patients with diagnosed macular edema at baseline should discontinue from the study.

Visit 4

At scheduled study visits the eye examination will include;

- ophthalmic history
- best corrected visual acuity measurement
- ophthalmoscopy (may include contact lens biomicroscopy to examine the macula and optic disc).
- measurement of central foveal thickness by OCT (required for all patients regardless of the results of visual acuity or ophthalmoscopy).

N.B. Ophthalmic findings should be recorded.

During the study if there are complaints of decreased vision or identification of worsening visual acuity (equal to or more than two lines on a standard eye chart using best corrected vision) then an unscheduled ophthalmic exam should be performed at which the eye examination will include;

- best corrected visual acuity measurement
- ophthalmoscopy (may include contact lens biomicroscopy to examine the macula and optic disc).
- measurement of central foveal thickness by OCT

N.B. Ophthalmic findings should be recorded.

The OCT can be performed by referring ophthalmologists or neurologists with clinical training and expertise to assess structural measurement of retinal nerve fiber layer thickness, optic nerve head, and macular anatomy AND currently possess appropriate OCT equipment in-office.

In case of suspected macular edema based on the ophthalmoscopy or if a relevant increase of central foveal thickness is observed, then a fluorescein angiogram may be performed to diagnose and characterize macular edema (at the discretion of the ophthalmologist), if present.
